5.9.1. Aim 1 analyses

The primary analysis will use multiple logistic regression models where the main independent variable is a binary variable representing assignment to economic incentives for non-heavy alcohol use (yes vs. no). The model will additionally control for assignment to incentives for IPT adherence (yes vs. no) and randomization stratification factors (i.e., gender and study cohort), to improve efficiency, and potential confounders not balanced on randomization.

The secondary outcome of treatment discontinuation due to hepatotoxicity will be analyzed using the same approach. However, if the number of hepatotoxicity events is sparse, the penalized likelihood method will be used.¹⁸¹ We will conduct similar analyses using INH adherence >90% as the outcome to evaluate whether there is an impact of economic incentives for decreasing alcohol use on IPT adherence. We will use linear regression models to examine continuous secondary outcome variables such as PEth levels, and will explore transformations for variables that are not normally distributed. If an appropriate transformation is not identified, a median regression model will be used.^{182,183}

Statistical power: With 680 participants enrolled, we anticipate 612 participants will complete both 3- and 6-month follow-up (i.e. 10% loss to follow-up). Assuming 2-sided tests, with an overall significance level of 0.05, and that 15% of controls will have no heavy drinking based on our prior data, the proposed study has 80% power to detect an absolute difference of 10% (i.e. 25% vs. 15% in the intervention and control arms, respectively) in the proportions with no heavy drinking using a chi-square test with continuity correction.

5.9.2. Aim 2 analyses

Similar to the analyses for Aim 1, multiple logistic regression models will be used to analyze the primary analysis of IPT adherence >90%, where the main independent variable is assignment to incentives for IPT adherence (yes vs. no). The model will also include a variable for assignment to economic incentives for decreasing alcohol use (yes vs. no) and randomization stratification factors, as above, and potential confounders not balanced on randomization. Continuous secondary outcomes (i.e. hair levels of INH and % doses taken across 6 months based on MEMS) will be analyzed using multiple regression models as described above.

Statistical power: Based on studies showing poor completion of IPT among drinkers,^{35,184} we conservatively assume 50% in the control group will achieve this outcome. With 612 evaluable subjects, the proposed study has 80% power to detect an absolute difference of 12% (i.e. 62% vs. 50% in the intervention and control arms, respectively) in the proportions completing >90% of IPT using a chi-square test with continuity correction.

5.9.3. Aim 3a analyses

We will use multiple logistic regression models including variables to represent the study arms and will also adjust for gender and study site (randomization stratification factors) to improve efficiency, as in Aims 1 & 2. The 3 pairwise comparisons of primary interest are between each intervention (Arms 2, 3, and 4) vs. control (Arm 1) and we will adjust for the multiple comparisons using the Hochberg sequential test procedure.¹⁸⁵ A secondary outcome of interest is virologic suppression at trial completion, analyzed using the same approach as above.

Statistical power: We expect 15% loss to follow-up at 6 months post-trial. We assume a conservative analysis based on a Bonferroni adjustment for multiple comparisons. For an overall type I error rate of 5%, we assume each of the 3 pairwise comparisons will be conducted at an alpha level of 0.0167. We expect that 67% of participants in the control group will have viral suppression at 6 months post-trial (SEARCH data). Given this assumption, the proposed study has 80% power to detect an absolute difference of 17% in the proportions with undetectable viral load for any of the 3 comparisons of interest (e.g., 84% vs. 67% in Arms 2,3, and 4 versus Arm 1, respectively) using a chi-square test with continuity correction.

5.9.4. Aim 3b analyses

We will explore reductions in alcohol use and level of IPT adherence as potential mediators that may drive the interventions to improve HIV virologic suppression. Thus we will evaluate whether a) reduction in alcohol use is related to virologic suppression; b) the interventions are related to reduction in alcohol use; c) the interventions are related to virologic suppression; and d) the effect of the interventions on virologic suppression reduces appreciably when reduction in alcohol use is added to the model.¹⁸⁶ However, because interpretation of the degree of mediation in logistic models (e.g. for the binary outcome refraining from heavy drinking) is complicated by their inherent nonlinearity, we will conduct additional analyses using a causal inference approach to mediation that derives direct and indirect effects for

binary outcomes.¹⁸⁷⁻¹⁹⁰ We will use the Stata mediation package to conduct these analyses.^{191,192} In addition to alcohol, we will also assess whether IPT adherence level is in the causal pathway between the interventions and viral suppression.

5.9.5. Additional analyses

Intervention effects over time. For Aims 1 & 2, we will conduct secondary analyses to assess intervention effects separately at 3 and 6 months and to assess for possible intervention by time interactions. We will use generalized linear mixed effects models that include subject-specific random intercepts and slopes for continuous outcomes and generalized estimating equations (GEE), with an independence working correlation matrix and logit link for dichotomous outcomes. Additional analyses will also be performed using mixed effects logistic regression models for correlated binary outcomes.

Moderators. We will perform additional analyses to explore potential moderators of the incentive interventions. For Aims 1 and 2, the potential moderators of interest are: sex, baseline level of alcohol use, readiness to change, and discount rate. Although we do not expect interaction between the two interventions, we will assess and test this as well. For each aim, we will fit separate models including 2-way interactions between randomization group and each potential effect moderator, as well as a model testing the interaction between the two interventions. If an interaction is significant, subsequent stratified analyses will be conducted to explore the effect of the economic incentives intervention by categories of the moderator.

Missing data. Participants who meet eligibility criteria and enroll in the study will be compared with eligible participants who decline enrollment, using the 2 independent samples *t*-test and Fisher's exact test. We will similarly test for differences between participants lost to follow-up and those who complete the study. In addition, data collected to the point of lost to follow-up will be compared to the data of those who complete the study to examine missing data mechanisms. In situations where missing data occurs, we will document the reasons for the missing data whenever possible. If it is reasonable to assume that data are missing at random, multiple model based imputation methods^{193,194} will be applied if needed.

6. Safety considerations

6.1. Potential Risks

Potential risks to participants, and their likelihood and seriousness to the human subjects: The potential risks associated with the study are risks due to study drugs, loss of confidentiality, stress from the study interviews, and risks associated with blood draws, including pain and, rarely, infection and/or bruising. The risks are described in detail below:

- **Medication risks**
 - **INH:** Serious side effects are: an allergic reaction (difficulty breathing; closing of the throat; swelling of the lips, tongue, or face; or hives); unusual weakness or fatigue; nausea, vomiting, or loss of appetite; abdominal pain; yellow skin or eyes; dark urine; numbness or tingling in hands or feet; seizures; blurred vision; confusion or abnormal behavior. (Source: <http://www.rxlist.com/isoniazid-drug/patient-images-side-effects.htm>). Very recent data from a randomized trial presented at the 2018 Conference for Retroviruses and Opportunistic Infections (CROI) found an increased risk of adverse pregnancy outcomes among HIV-positive women taking INH during pregnancy compared to HIV-positive women who initiated INH post-partum. (Source: <http://www.croiconference.org/sessions/randomized-trial-safety-isoniazid-preventive-therapy-during-or-after-pregnancy>). Recently, following a country-wide scale-up of INH in Uganda ("100-day push"), several clinics reported cases of death thought to be a result of liver failure, possibly attributable to INH-drug-induced liver injury. Anecdotally, the deaths appear to have occurred primarily in patients who started on INH and Dolutegravir at the same time. The deaths occurred in clinical settings with limited laboratory (LFT) monitoring. In response, the Uganda MoH and Uganda National Drug Authority (NDA) have set up a pharmacovigilance plan and had a visit from members

of the World Health Organization, to consider a response to these clinical observations. In July 2020, the Uganda MoH revised their Consolidated Guidelines for the Prevention and Treatment of HIV to advise delaying initiation of IPT for individuals who have newly initiated on DTG (within three months).

- **Vitamin B-6:** Most common side effects include: nervous system abnormalities (such as tingling feelings, shooting pains, numbness, and not being able to feel pain or temperature). (Source: <http://patient.info/medicine/pyridoxine-tablets>).

Study participants will be given information on the TB preventive therapy (INH) as well as Vitamin B-6. Participants will also be given instructions on how to use the MEMS device. The study staff will be trained to assess for all possible side effects of INH and Vitamin B-6 and will follow established protocols for identifying and monitoring any ongoing adverse events, including referrals to treatment. Study participants will be actively monitored for adverse events, particularly those related to INH, and Vitamin B-6 as in the most recent FDA's Drug Safety Announcement. Symptoms will be assessed at each follow-up study visit for the duration of treatment (at 2 weeks, 1, 2, 3, 4, 5, and 6 months), and additionally at 7 months, as needed for those who develop hepatotoxicity. RAs will document hepatotoxicities and side effects on CRFs, completed in real-time, as they receive the information from the participants, and submit completed forms to the study physicians for weekly review.

Other risks

- **Tuberculin Skin Testing (TST):** Risks of TST testing with subcutaneous placement of purified protein derivative (PPD) are rare, but include a very low risk of a severe allergic reaction to the skin test (<https://www.cdc.gov/tb/publications/factsheets/testing/skintesting.htm>). Participants with a history of a severe reaction to a TST in the past will not be given a TST during this study.
- The loss of confidentiality may lead to disclosure of HIV infection, TB infection, or disclosure of drinking status. Stigma associated with such disclosure may include social harms such as disruption of family (e.g., breakup of couples following HIV detection in one spouse), discrimination (e.g., a loss of employment or status in community), physical harm such as domestic violence (e.g., acts of physical violence directed at people who have been diagnosed with HIV), and psychological harm such as embarrassment (e.g., being questioned by family members about alcohol use). There may be some discomfort with the nature of the interviews, since alcohol use will be discussed. There is also the very slight but present chance of a breach of confidentiality inherent in any study that handles confidential data.
- Psychological stress could be caused by the interview in which participants will be asked sensitive questions regarding substance use and HIV status and progression. Distress caused by the length of the interview is also possible. The RAs will be trained to address these issues with a calm, non-judgmental attitude. These minimal risks are not likely and will be minimized further by only selecting patients who understand the study and are willing to participate.
- Phlebotomy associated risks include bruising, bleeding, infection, phlebitis, and pain. Bruising is common, minor pain with needle stick is universal, the other risks are rare.
- **Hair Collection:** The risk of a cut to the skin from scissors during hair collection is extremely low. We have been collecting small hair samples from HIV-positive participants on antiretroviral therapy in the NIH-funded Women's Interagency HIV Study (WIHS), a large multicenter prospective study of HIV-infected and at-risk HIV- uninfected women, every six months since 2002. We have collected over 20,000 hair specimens in the WIHS via the collection procedure outlined in the research plan above and have never had an injury or any other adverse event reported from the collection process.

The risk of cosmetic effects from hair collection is also extremely low. The human scalp loses an average of 100 strands of hair per day, so the amount of hair we propose to collect for this project is less than what a participant's scalp would typically lose on an average day. Moreover, the size of the hair sample collected for the INH assays is extremely small and collection is usually easily accomplished from participants with short or limited amounts of hair. Over the past 12 years of collecting hair from participants in the WIHS cohort, we have never registered any complaints that the process has been disruptive to hair styles and we have high rates of acceptability of hair collection in the overall study (ranging from 88-97%, depending on the site). We have also been collecting hair from HIV-infected women and their infants in Uganda ([name] PROMOTE study), HIV infected pregnant women in South Africa, and participants in several pre-exposure prophylaxis (PrEP) trials. We have experienced high rates of acceptability of hair collection in each of these studies (~95%), have not registered any reports of adverse events, including accidental skin cuts or disruption of hair styles, in any of these studies.

- Biohazard exposure is an additional risk, as the transmission of HIV and other blood-borne pathogens can occur through contact with contaminated needles, blood, and blood products. Personnel will be trained in and follow standard laboratory procedures to minimize the risk of contamination.
- Another risk stems from the use of economic incentives, which might be viewed as coercive. However, the expected value of the economic incentives at each visit (taking into account low probabilities of high value awards) is relatively low (US\$5 per lottery draw). A recent publication by the Ethics Working Group of the HIV Prevention Trials Network (HPTN) has also made the case that the use of incentives for health promotion does not necessarily undermine individual autonomy.¹⁹⁵ Instead, incentives can help overcome economic obstacles or motivational deficiencies; they can promote engagement in health-related behaviors that participants regard as beneficial or worthwhile, but do not undertake due to behavioral biases such as present-biased preferences or delayed reward discounting. Our past experience implementing economic incentive interventions in Kenya and Uganda has also demonstrated that such interventions are acceptable to both communities and ethical review boards.

Alternative procedures: The alternative is to either not consent to the study or to withdraw from the study at any time after consented. We will be clear with participants that there is no obligation to enroll in or continue with the study. Any participant may decline any study procedure at any time—this will not affect the person's ability to receive care at any HIV clinic. Any potential study participant who does not wish to enroll in the study but wishes to learn more about their alcohol consumption will be referred to their doctor.

6.2. Protection against risks

All adverse events (AEs): The Field Coordinator will complete descriptions of AEs on an AE reporting form that will be sent promptly to the Principal Investigator (PI) and all study investigators. Additionally, AEs will be reported to the Data and Safety Monitoring Board (see below), which will conduct further review of data from the DIPT Study and re-evaluate the risks to the participants.

Planned procedure for protection from risks due to medications: Study participants will be given information on the medication and advice on how to take the prescribed medications. They will be advised on the dosage and told not to double up on pills if any are missed. The staff will be trained to assess for all possible side effects of the medications and will follow established protocols for identifying and monitoring any AEs. Study participants will be actively monitored for AEs, particularly those related to INH and Vitamin B-6. Symptoms will be assessed at each follow-up study visit (at 2 weeks, and 1, 2, 3, 4, 5, and 6 months; 7 months as needed for those who develop hepatotoxicity.) by a trained clinical officer, and participants will be trained to recognize symptoms of hepatotoxicity. ALT/AST testing will also occur at these visits. Results of the ALT/AST testing will be given to the RAs by each cohort's research laboratory within 24 hours of testing. All participants will be given the phone number of the clinical officer to call in case symptoms develop between visits. In the case of suspected toxicity, the clinical officer will notify one of the two study physicians, who will determine whether a Grade 3/4 toxicity has occurred, and will recommend stopping treatment if INH is considered the

cause. The physicians will be blinded of the participant's study arm. If hepatotoxicity is discovered by ALT/AST results after the patient has left the clinic, the RA will contact the participant immediately via phone to inform them, and will make a follow-up home visit to retrieve the dispensed medications from the participant. In addition, the clinical officer will notify the study clinic for continued patient follow-up. Study participants will remain in the study following treatment discontinuation for follow-up monitoring, but will no longer be eligible to receive incentives for positive IsoScreen urine tests.

Women of childbearing age will be asked about possible pregnancy at each follow-up study visit for the duration of INH treatment (at 2 weeks, 1, 2, 3, 4, 5, and 6 months), and additionally at months 7-9, for those who do not complete the regimen within the first 6 months. Women who report that they may have become pregnant will be offered a urine pregnancy test. Women who are confirmed to be pregnant will be discontinued from INH treatment. Study participants who become pregnant will remain in the study following treatment discontinuation for follow-up monitoring, but will no longer be eligible to receive incentives for positive IsoScreen urine tests.

Individuals who are prescribed Dolutegravir (DTG) will not be enrolled into the study until they have been on DTG for at least 3 months, to prevent starting DTG and INH at the same time.

Participants who are discontinued from INH treatment (due to toxicities or pregnancy) may still be eligible to receive incentives from EtG testing if they are in study arms 2 or 4.

Planned procedure for protection from risks due to phlebotomy: Trained RAs (trained clinical officers) or laboratory technicians will collect all specimens using standard sterile procedures. The phlebotomist will report any complications resulting from blood draws to the field study coordinator, who will make an immediate report to the Principal Investigator. The Principal Investigator will take responsibility for reporting such AEs to the relevant IRBs and NIH within ten days.

Planned procedure for protection from risks due to TST: The RAs (trained clinical officers) will conduct the TST in participants using standard sterile procedures. RAs will report any complications resulting from the TST to the field study coordinator, who will make an immediate report to the Principal Investigator. The Principal Investigator will take responsibility for reporting such AEs to the relevant IRBs and NIH within ten days.

Planned procedure for protection from risks due to alcohol use: During our study assessments, we may uncover probable alcohol dependence, using an AUDIT-C score of 8 or more. In this case, or at the participant's request over the course of the study, we will continue with study activities but also refer patients [to their clinicians at the study clinics for DIPT 1/2 / to the treating clinicians at the SEARCH study clinics for DIPT 2/2](#). In addition to the referrals, we will offer brief alcohol counseling to participants enrolled in all study arms at the baseline study visit as part of standard of care.

Planned procedure for protection from risks due to lack of biohazard containment: As the transmission of HIV and other blood-borne pathogens can occur through contact with contaminated needles, blood, and blood products, appropriate blood and secretion precautions will be employed by all personnel in the drawing of blood and shipping and handling of all specimens for this study, as currently recommended by the Centers for Disease Control and Prevention and the NIH.

Planned procedure for protection from risks due to use of economic incentives. It will be explained to participants that incentive payments will be conditional on the specified behavior (reduced alcohol use and/or INH adherence), and that the expected value of each lottery card is approximately US\$5. Coercion is unlikely in this case because the incentives are not so large in value that they exceed the likely costs associated with retention in care and meeting the desired health behaviors.

Planned procedures for the protection of loss of confidentiality: The primary risk of participating in this study is the loss of confidentiality. While many participants in our current studies have disclosed their HIV status to their family, we consider loss of confidentiality an important risk of the study and have implemented the following procedure to reduce the risk to confidentiality.

- We will discuss the possibility of HIV, TB, or alcohol-related stigma with the potential participants during the informed consent process for the study. We will ask potential participants to think about persons in their family, group of friends, neighborhood, or workplace, who don't know their HIV or TB status, and how they might react to discovering that the participant is infected with HIV or TB, or drinks alcohol. Enrollment will be deferred for those who are unsure about ramifications of participating. Persons who decline or defer enrollment in the study will be assured that this will not affect their HIV care.
- We will ensure that all study visits and telephone calls for tracking or study visit reminders, may be deferred for any reason and that participation in the study may be ended at any time. Telephone calls may be ended at any time with a pre-agreed upon word or action.
 - Study staff will be trained to apply the same measures of confidentiality and sensitivity during phone calls as they do with all other data collection activities.
- We will provide referrals to all participants and persons considering enrollment to social support services provided by the MRRH Counseling Program or other equivalent counseling program available in the area, as desired. These services include the option of participating in support groups where issues of disclosure can be discussed, and the individual can learn from peers about high-risk disclosure situations and how to minimize risk.
- To ensure confidentiality of participation, all instruments, forms, and biologic specimens will be coded with a unique participant identifier that renders the data anonymous to persons outside the study. All data will be kept in locked cabinets and on secure servers. Research records will be kept confidential to the level allowed by law. Records with identifying information, such as contact information and consent forms, will be stored separately from survey information. No individual identities will be used in any reports or publications.
- All staff in contact with participants and/or data will be trained on procedures for maintaining privacy and will sign a pledge of confidentiality. They will also take CITI human subjects training courses.
- We will provide participants with information on how to contact the local field staff to report incidents such as HIV-related disruption of families, acts of discrimination, and physical harm. This information will also be written on the take-home consent form.

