5.2.2. Exclusion criteria

Exclusion criteria for all sites will include:

- a) Prescribed nevirapine (NVP, an ART drug that is declining in usage due to high risk for hepatotoxicity);
- b) Initiating Dolutegravir (DTG), or has initiated DTG within the past 3 months;
- c) Plans to move out of the catchment area within 6 months;
- d) Prescribed anti-convulsion medications or history of recurring seizures;
- e) ALT or AST elevations ($\geq 2 \times$ ULN);
- f) Suspected or confirmed active TB as determined by symptom screening and followed by chest X-ray and sputum testing;
- g) History of prior active TB treatment or prior IPT.
 - As fewer than 3% of HIV-infected persons have received IPT in Africa, prior IPT will be rare.¹⁴⁴
- h) Pregnant at the time of screening
- i) Gross inebriation or inability to provide informed consent.

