Key points to check with the participants enrolling in the trial include: (1) they will be asked to undergo blood collection via venipuncture, provision of a small hair sample at 3 and 6 months after enrollment, and research assessment procedures; (2) they will be asked to repeat blood specimen collection, and urine collection (if in Arms 2, 3 or 4) and research assessment procedures at follow-up visits (week 2 and months 1, 2, 3, 4, 5, and 6 and 12) following enrollment; (3) some participants will be randomized to be eligible to receive incentives based on point-of-care urine tests that meet pre-specified criteria; (4) they will be asked to provide their name and locator information to allow the investigators to locate them for future visits; (5) they will receive a reminder call prior to their study visits; (6) they may be removed from INH if they become pregnant or develop toxicities (Grade 3 or 4); and (7) they may be asked to participate in further studies in the future.

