5.5. Study visits

As previously described, eligibility will be a two-stage process in order to determine drinking status, TST status, and rule out active TB and liver enzyme elevations. Baseline visits will include collection of tracking information, a baseline survey (Table 2), blood draw, and repeat liver enzyme testing if it has been longer than one month from the screening tests.

[figure not shown]
Visits for INH refills and assessments for toxicity (assessment of side effects and liver enzyme testing) will occur at week 2 and months 1 through 6 for all study participants. Urine will be collected and prizes administered as described above for Arms 2, 3, and 4. Hair collection will occur at 3 and 6 months c at the time of the INH discontinuation if outside of the 3- and 6-month time point for all study participants (see below). Follow-up interviews and blood collection will occur at months 3, 6, and 12 (Table 2). Screening for symptoms of active TB, and sputum testing and chest X-ray if symptoms are reported, will occur at every follow-up visit.

Arms 2-4 only: Urine test(s) and prize(s)
↓
Month 12: Study survey, Blood draw (PEth, VL)

Retention: High retention (90% at six months, 85% at one year) will be maintained as in our prior studies using follow-up phone calls, alerts when patients come to their home clinic, and home visits when needed. To encourage high retention, participants in all study arms, including control, will receive travel reimbursements (low-value unconditional cash transfers) of up to US\$5 for attending study visits (see Figure 3).

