Missed or late visits: If a participant misses a scheduled visit, the visit will be rescheduled within the coming 4 weeks after the missed visit, and missed visits (i.e. no-show for a clinic appointment >3 days after the scheduled clinic appointment date) will automatically prompt an incentive “reset” to baseline (i.e. drawing one card only if the incentive condition is met). Late or early visits, defined as coming to an appointment more than 3 days of an assigned appointment date, will result in an incentive “reset” to baseline. On rare occasion, exceptions to the protocol for early, late, and missed visits may be considered at the discretion of the study coordinator and study PIs. All participants will be allowed up to 9 months from INH initiation to complete a 6-month course (180 tablets) of INH, taking missed visits/refills into account. Participants that miss ≥3 months of visit time will be considered as having failed to complete IPT.

Figure 3. Study visit flow chart: Aims 1, 2 & 3.

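### The dolutegravir rule acts only at enrolment; the protocol states no check for, or physician alert to, a dolutegravir start soon after isoniazid begins

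*Protocol*

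**What the plan says.** **Entry rule.** Exclusion (b) in Protocol section 5.2.2 reads "Initiating Dolutegravir (DTG), or has initiated DTG within the past 3 months". Section 6.2 repeats it as a condition of enrolment (at least three months on DTG first) and states the aim: "to prevent starting DTG and INH at the same time".

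**Background.** Section 6.1 reports deaths during a national INH scale-up. It describes as anecdotal the link to patients who began INH and DTG together, and says liver testing was limited where the deaths occurred. It cites July 2020 national guidance to delay preventive therapy in people who began DTG within the previous three months.

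**After enrolment.** Section 5.5 says that INH refill visits and "assessments for toxicity (assessment of side effects and liver enzyme testing) will occur at week 2 and months 1 through 6". It adds: "Follow-up interviews and blood collection will occur at months 3, 6, and 12". Sections 6.2 and 6.4 have the clinical officer notify a study physician, blinded to arm, when toxicity is suspected.

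**Gaps.** Section 5.5 says: "All participants will be allowed up to 9 months from INH initiation to complete a 6-month course". Missing three or more "months of visit time will be considered as having failed to complete IPT".

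**Comparison within section 6.2.** Pregnancy, also an entry exclusion, is asked about at every follow-up visit on INH and at months 7 to 9 for late completers. A confirmed pregnancy stops INH.

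**The concern.** The stated purpose concerns two drugs starting together, whichever comes first. The control covers one order only: DTG first, then INH. Participants must have had at least six months of antiretroviral therapy, so a later DTG start would be a regimen switch made by the HIV clinic. Exclusion (b) shows that the protocol expects such switches before entry. Nothing in the documents suggests that they end at enrolment.

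Two routes are left open:

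1. A participant on another regimen begins INH, and the clinic starts DTG within days.
2. A participant starts DTG during a permitted INH gap and then resumes INH.

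At stake is a chance to prevent harm rather than detect it. All participants are heavy drinkers, whom section 3 treats as being at raised risk of INH liver injury. The monitoring finds injury once enzymes or symptoms change. As written, nothing tells the physician beforehand that DTG has just been started, so INH cannot be held, or enzymes tested early, for that reason. No effect on a primary outcome, power or type I error is claimed.

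**Working it through.** The plan gives no figure for this point. The check is a reading of both documents plus simple counts.

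**Where DTG appears.** It appears in Protocol sections 5.2.2, 6.1 and 6.2, and nowhere in the SAP. The operative text (5.2.2 and 6.2) acts at enrolment. Section 6.1 is background.

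**What is checked on INH** (Protocol section 5.5 and Table 2).
- Scheduled visits on INH: week 2 plus months 1 to 6 = 1 + 6 = 7.
- ALT/AST: 7 of 7.
- Study interview: months 3 and 6 = 2 of 7 (month 12 falls after INH).
- Stated question or record check on a new antiretroviral drug: none found.
- Trigger for physician notice: suspected toxicity.

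**Longest wait from a DTG start to the next scheduled ALT/AST** (30-day months assumed).
- Day 0 to week 2: 14 days.
- Week 2 to month 1: 30 − 14 = 16 days.
- Month to month after that: 30 days.

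The corresponding wait to the next interview is up to 90 days (baseline to month 3, or month 3 to month 6). That figure matters only if the interview asks about regimen, which the documents do not show.

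**Gap route.** The SAP counts doses within a 270-day window against 180 prescribed doses, so total slack is 270 − 180 = 90 days. A gap short of failure is under three months. DTG begun inside such a gap is no older than the gap, so it is under three months old when INH resumes. A person with that DTG history could not have enrolled. The 90 days is a total allowance, not a typical gap: section 5.5 reschedules missed visits within 4 weeks.

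**Evidence that INH interruptions occurred.** The SAP's paragraph on COVID-related disruption says participants on INH were told to stop when activities paused on 19 March 2020. Visits resumed on 26 May 2020: 12 + 30 + 26 = 68 days. The SAP does not say who resumed INH, so this is an illustration only.

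**Months 7 to 9.** Listed symptom and enzyme visits end at month 6, with month 7 as needed after hepatotoxicity. INH may run to month 9. Section 5.6 ties same-day ALT/AST to the safety of refills, so later refills and restarts may still be tested.

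**Number at risk.** The documents give neither the share of participants off DTG at entry nor a switch rate, so no count can be derived.

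**The case against.** **The guidance is narrower.** A reader might infer that the trial departs from national guidance. It does not. As described in section 6.1, the guidance is about delaying initiation of preventive therapy after new DTG, and the entry rule follows it. It does not address DTG started after INH, and resuming INH after a gap is not initiation. This stands: the extension to both routes rests on the protocol's own statement of purpose, and the gap route is the weaker of the two.

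**Monitoring is strong.** Route 1 falls where checks are closest together (week 2 and month 1). A restart after missed refills carries same-day ALT/AST. There is a phone line between visits, home retrieval of INH when toxicity is found after the visit, advice to hospitalise above 10 times the upper limit of normal, and a hepatologist on the monitoring board. The reported deaths came from settings with limited testing. This stands and keeps the point minor, but these steps detect or manage injury and do not report a new exposure.

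**Silence is weak evidence.** Tables 2 and 3 also list no regimen item at screening, although exclusion (b) and exclusion (a), "Prescribed nevirapine (NVP, an ART drug that is declining in usage due to high risk for hepatotoxicity", both need one. The tables are therefore not a full list of what is recorded. Operating procedures, case report forms and questionnaires were not supplied. Section 4.1 describes electronic clinic and pharmacy records at one site and digitised clinic records at the other. A regimen check may exist in any of these. This stands as a limit.

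**Stopping reasons.** The consent points say "they may be removed from INH if they become pregnant or develop toxicities (Grade 3 or 4", and section 6.2 names the same two reasons. A reader might infer that INH could be stopped for nothing else. The SAP's lockdown account rules that out: INH was stopped as a precaution because liver monitoring was not possible.

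**Conclusion.** The point holds as a minor, low-cost safety improvement. The DTG rule acts only at enrolment, although its stated purpose is broader. The supplied documents state no check for a DTG start soon after INH begins, and physician notice depends on suspected toxicity. The gap route is a secondary concern.

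The conclusion assumes that the purpose in section 6.2 is meant to hold after enrolment, and that no unsupplied procedure already covers it. If one does, a cross-reference in section 6.2 would largely settle the matter. Its size is unknown; the schedule bounds only the wait to the next scheduled enzyme test, at 14 to about 30 days.

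A reader might also infer that any DTG switch during INH defeats the rule. A switch well after INH is established, with no gap, is a different sequence from the simultaneous start the rule names, and the documents do not support treating it as a breach.

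**What to change.** In Protocol section 6.2 and the visit schedule:

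- At each existing INH visit, including months 7 to 9 for late completers, ask about any antiretroviral change (drug and start date), or check the clinic record. Section 6.2 already uses this pattern for pregnancy.
- Do the same before INH is resumed after a gap.
- Notify the arm-blinded study physician the same day of any new DTG start. The physician decides whether to hold INH or repeat ALT/AST early; no automatic stop is proposed. The alert reports regimen, not arm, so blinding is kept.

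The cost is one question or record check and one alert step, with slightly longer refill visits.
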